### **2.7.7 Growth and Development**

**Growth velocity** will be listed at EOT-extension visit and summarized using descriptive statistics by sex and age group during the entire granule period for the Safety Set 4. Listing will be produced for the entire granule period on the Safety Set 4.

The growth velocity in height which evaluates the rate of growth per year will be calculated on the difference with the previous measure of height (in cm) and the time period (in days) as:

$$\text{Growth velocity (cm / year)} = \frac{(height V_x - height V_{x-1}) * F}{date V_x - date V_{x-1}}$$

(with  $V_x$  = actual visit ;  $V_{x-1}$  = previous visit ;  $F = 365.25$ ).

### 2.7.7.1 SDS method

**Growth data** collected during the study (both core and extension phases) for safety set 4 subjects will also be summarized descriptively at each relevant time point. These data consist of BMI, height, height velocity, weight and weight velocity.

The baseline for this analysis will be the core phase baseline for both DT crossover and granule patients.

Height and BMI will be summarized at 6 months intervals, using the standard deviation scores (SDS, also called z-score), velocity and velocity SDS. The relevant height and weight values for each 6-month period are defined using time windows, as defined in [Section 5.3.3](#). The z-scores will allow identification of potential outliers.

The formula used to calculate the SDS and height and weight velocities are provided in [Section 5.6](#).

Note that BMI SDS are reported instead of weight SDS as no reference data for weight are provided by the WHO for age beyond 10.

Height/BMI SDS and height/weight velocity SDS will be summarized using descriptive statistics (mean, standard deviation, range) for each time window (at Baseline and thereafter allowing informal comparison of growth data), as well as by presenting number of patients with SDS values lower/higher than 5th/95th percentiles respectively. Box plots will also be plotted for each time window. In addition, a shift table to compare baseline SDS to the worst on-treatment SDS will be produced for height and BMI SDS. All height/BMI SDS, velocity and velocity SDS data will be listed, and values of SDS and velocity SDS outside of the central 95% of population values will be flagged as either High (SDS > 1.645) or Low (SDS < -1.645).

### 2.7.7.2 Pubertal Stage

**Pubertal stage** assesses the stage of physical development of sex characteristics. The characteristics breast development, pubic hair, testes and penis size are evaluated based on the Tanner scale: for each characteristic there are 5 classes (Tanner stage 1 to 5) indicating the level of development of that specific characteristic.

The age will be summarized descriptively at baseline and each annual assessment for the entire granule period by sex, characteristic, Tanner stage and treatment arm (core phase and extension phase displayed separately).

A listing will be provided including the Tanner stage as well as the individual records for each sex characteristic by visit. Patients with delayed puberty will be flagged in the listing. Delayed puberty in boys is defined as failure to attain Tanner Stage 2 (for both testis and pubic hair) by

age 14 (Crowley and Pitteloud 2012) and in girls is defined as the failure to attain Tanner Stage 2 (for both breast development and pubic hair) by age 13, or absence of menarche by age 15 or absence of menarche within 5 years of attainment of Tanner Stage 2 (Fenichel 2012).

## 2.7.8 Other safety data

### 2.7.8.1 Cardiac evaluations

Cardiac evaluations include ECG and echocardiogram. Any abnormalities at baseline were analyzed for the primary CSR analysis and will not be repeated for the final CSR. All findings of patients with new or worsened abnormalities since baseline will be listed separately for Safety Set 4.

### 2.7.8.2 Vital signs

The following criteria define clinically notable abnormalities for vital signs and weight values:

**Table 2-5** Definition of clinically notable abnormalities for vital signs and weight values

Parameter 			
Weight	High	Increase from baseline ≥ 10%	
	Low	Decrease from baseline ≥ 10%	
Pulse rate (beats per minute)	High 	12-18 months > 140	
		18-24 months > 135	
		2-3 years > 128	
		3-4 years > 123	
		4-6 years > 117	
		6-8 years > 111	
		8-12 years > 103	
		12-15 years > 96	
		15-18 years > 92	
	Low 	12-18 months < 103	
		18-24 months < 98	
		2-3 years < 92	
		3-4 years < 86	
		4-6 years < 81	
		6-8 years < 74	
		8-12 years < 67	
		12-15 years < 62	
		15-18 years < 58	

 Systolic and diastolic blood pressure will be listed individually.

Descriptive statistics will be tabulated per time window and treatment arm using absolute change from baseline values for each vital sign measure, weight and BMI (see [Table 5-4](#) for time windows definition) separately for Safety Set 4.

All vital sign assessments, weight and BMI will be listed by treatment arm, patient and parameter. In the listings, clinically notable values will also be flagged.

### 2.7.8.3 Other data

All data from auditory evaluation, hepatitis testing, and pregnancy test will be listed.

Patients with clinically significant abnormal interpretations or abnormal values will be flagged as well as positive pregnancy test results.

Data related to blood transfusion during treatment phase will be listed by treatment arm.

## 2.8 Pharmacokinetic endpoints

The assessment of pharmacokinetic parameters was characterized in the primary CSR and will not be repeated for the final CSR. For details on this analysis, refer to the primary analysis SAP.

## 2.9 PD and PK/PD analyses

The exposure-efficacy relationship was characterized in the primary CSR and will not be repeated for the final CSR since no additional data was collected for these endpoints after the primary CSR data cut-off. For details on this analysis, refer to the primary analysis SAP.

## 3 Sample size calculation

Refer to Section 2.11 of the primary analysis SAP for details

## 4 Change to protocol specified analyses

**Table 4-1 Changes to protocol specified analysis or descriptions and rationale**

Protocol section	Protocol description	Change	Rationale
10.5.4.1	Exposure-adjusted adverse event incidence, defined as number of patients with new or worsened AEs during period/[total number of days patient was on treatment summed for all patients/365.25 days], will be presented	Exposure-adjusted AE incidence will not be presented	Core phase duration is same for both arms and hence not generated for safety set 3 in EoC CSR. No comparison planned between crossover to DFX Granule in DT arm and DFX Granule arm for entire granule

---

period in safety set 4  
irrespective of  
heterogenous follow-  
up.

---

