#### **10.5.4.1 Adverse events (AEs)**

Summary tables for adverse events (AEs) have to include only AEs that started or worsened during the on-treatment period, the treatment-emergent AEs. However, all safety data (including those from the pre and post-treatment periods) will be listed and those collected during the pre-treatment and post-treatment period are to be flagged.

The incidence of treatment-emergent adverse events (new or worsening from baseline) will be summarized by system organ class and/or preferred term, severity, type of adverse event, relation to study treatment by formulation group. Exposure-adjusted adverse event incidence, defined as number of patients with new or worsened AEs during period/[total number of days patient was on treatment summed for all patients/365.25 days], will be presented.

An overall summary of type of AEs (e.g. serious, leading to study drug discontinuation, requiring dose adjustment or/and interruption) will be presented by severity and formulation group.

Specific groupings of adverse events of special interest will be considered and the number of patients with at least one event in each grouping will be reported. Such groups consist of adverse events for which there is a specific clinical interest in connection with Deferasirox treatment or adverse events which are similar in nature (although not identical). Note that certain adverse events may be reported within multiple groupings/AESIs.

AESIs are defined by MedDRA terms. All AESI definitions or AE groupings are specified in the Novartis electronic Case Retrieval Strategy (eCRS). The latest version of the eCRS available at the time of the analysis will be used.

Incidence of AESI will be summarized by grouping, preferred term and treatment arm.

Summary tables for adverse events (AEs) will be repeated for the optional extension phase on the Safety Set 4.

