**Table 2-1      Definition of core and extension phases**

[figure not shown]
Core phase			Extension phase		
Treatment	Start date	Stop date	Treatment	Start date	Stop date
Granules	Date of first IC signed	Date of last treatment of granules + 30 days	No treatment	Nil	Nil
DT	Date of first IC signed	Date of last treatment of DT + 30 days	No treatment	Nil	Nil
Granules	Date of first IC signed	date of first administration of granules in extension phase* – 1 day	Granules	date of first administration of granules in extension phase*	Date of the last administration of Granules in extension + 30 days
DT	Date of first IC signed	Date of first administration of granules* – 1 day	Granules	Date of first administration of Granules*	Date of the last administration of Granules in extension + 30 days

\*including 0 doses for patients to identify the extension start date only

Summaries will be based on:

- Entire granule period - patients randomized to Granules combining core and extension phases (dark green rectangle in [Figure 2-1](#)) side-by-side with Granules for patients randomized to DT who switched to Granules in extension phase (light green rectangle in [Figure 2-1](#)). Cross-over treatment group corresponds to the patients randomized to DT who switched to Granules in the extension phase.

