### **2.1.6 On-treatment period**

The overall observation period will be divided into three mutually exclusive segments taking into account stop rules as per [Table 2-1](#):

- Pre-treatment period: from day of patient's first informed consent to the day before first dose of study drug;
- On-treatment period: from day of first dose of study drug to 30 days after last dose of study drug.
- Post-treatment period: starting at day 30+1 after last dose of study treatment.

For the entire granule period, the following conventions will be taken into account while deriving the three observation periods above:

- For patients enrolled in DT formulation in the core phase, the pre-treatment period will not be derived, and their entire granule period starts from Extension phase start date mentioned in [Table 2-1](#)
- For patients enrolled in Granule formulation in the core phase, the first dose of study drug will be the day of first dose in the core phase.

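### The final SAP drops the protocol's exposure-adjusted AE incidence and shows crude percentages side by side for two granule groups whose follow-up clocks start at different points

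*SAP*

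**What the plan says.** Protocol Section 10.5.4.1 defines the measure as "Exposure-adjusted adverse event incidence, defined as number of patients with new or worsened AEs during period/[total number of days patient was on treatment summed" over all patients and converted to years, and commits to presenting it. The same section adds: "Summary tables for adverse events (AEs) will be repeated for the optional extension phase on the Safety Set 4".

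The final SAP (Section 4, Table 4-1) reverses this: "Exposure-adjusted AE incidence will not be presented". It gives two reasons. For the core phase: "Core phase duration is same for both arms and hence not generated for safety set 3 in EoC CSR". For the entire granule period: "No comparison planned between crossover to DFX Granule in DT arm and DFX Granule arm for entire granule" period in Safety Set 4. That sentence goes on to acknowledge that follow-up is heterogeneous.

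The removal is older than the final SAP. The document history of the primary-analysis SAP records it under version 3.0, dated 1 February 2017. Neither that SAP (Table 3-1, which lists no changes) nor the End of Core SAP (Table 3-1, which lists three other items) declares it as a departure from the protocol.

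Four provisions of the final SAP govern how AEs will be shown:

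- **Population and period** (Section 2.7): AE analyses use Safety Set 4 over the entire granule period. Safety Set 4 is everyone with at least one granule dose in the core or extension phase (Section 2.2).
- **Layout** (Section 2.1, text after Table 2-1): granule-arm patients, with core and extension combined, are shown "side-by-side with Granules for patients randomized to DT who switched to Granules in extension phase".
- **Clock** (Section 2.1.6): for the granule arm, "the first dose of study drug will be the day of first dose in the core phase". For cross-over patients the period begins at extension start.
- **Denominator** (Section 2.1.1): the number of patients in the arm.

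**The concern.** A percentage of patients with at least one event rises with time observed. Two groups with the same underlying rate will show different percentages if one is watched longer, and a single percentage that pools very different follow-up times is hard to read as long-term incidence even without a comparator. Extension time varies between patients by design, because it ends at local access to the new formulation or at 5 years (protocol Section 6.1.2).

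Additional safety data on granules is the stated objective of the extension, and it is the only objective in the final SAP's Table 1-1 marked for full reporting in the final report. Declaring that no comparison is planned does not stop a reader from comparing adjacent columns, and it does not turn a crude percentage into a rate that can be set against other data.

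**Working it through.** **1. Planned offset.** Core treatment lasts 48 weeks (protocol Section 6.1.2). The SAP's visit formula, study day (5 + 4k − 1) × 7 + 1, reproduces it:

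- k = 11: Week 49, day 337, which is 336 / 7 = 48 weeks after day 1.
- k = 75: Week 305, day 2129, which is 2128 / 7 = 304 weeks after day 1.

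Maximum planned granule time is therefore 304 weeks in the granule arm and 304 − 48 = 256 weeks in the cross-over group, a ratio of 1.19.

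**2. Effect on crude percentages.** Assumptions not in the documents: the same constant first-event rate r in both groups, everyone enters the extension, and a common extension of E weeks. The expected percentage is 1 − exp(−rT), with T = (48 + E) × 7/365.25 years for granules and E × 7/365.25 for cross-over. At r = 0.2 per patient-year:

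| E (weeks) | T granules / cross-over (years) | Granules | Cross-over | Ratio |
|---|---|---|---|---|
| 52 | 1.92 / 1.00 | 32% | 18% | 1.8 |
| 156 | 3.91 / 2.99 | 54% | 45% | 1.2 |
| 256 | 5.83 / 4.91 | 69% | 63% | 1.1 |

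Over rates from 0.05 to 1.0 and extensions from 52 to 256 weeks, the spurious gap runs from about 0.4 to 22 percentage points.

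**3. Does 48 weeks hold as a group difference?** Let p be the share of the granule arm entering the extension and c the mean core weeks of those who do not. The difference in mean follow-up is p(48 + E) + (1 − p)c − E. With c = 24 (assumed):

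- E = 108: p = 1 gives 48 weeks; p = 0.9 gives 34.8; p = 0.8 gives 21.6; p = 0.6 gives −4.8.
- E = 256: p = 0.8 gives −8.0 weeks.

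The crude percentages follow. At r = 0.25 and p = 0.8 they are 44.3% (granules) against 40.4% with E = 108, and 52.1% against 52.6% with E = 156. At p = 0.6 and E = 108 they are 35.9% against 40.4%. The distortion can point either way.

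**4. Would the protocol's formula repair it?** Its denominator is total treatment time, which keeps running after a patient's first event. Under the assumptions of step 2:

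- r = 0.10, E = 52: crude 17.4% against 9.5%; protocol measure 0.091 against 0.095 per year. Most of the artefact goes.
- r = 1.0, E = 108: crude 95.0% against 87.4%; protocol measure 0.318 against 0.422 per year. The true rates are equal, but the formula now makes the longer-followed group look better.

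With person-time to first event, the expected denominator per patient is (1 − exp(−rT))/r. Patients with an event divided by this is r in both groups, whatever T is.

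**The case against.** The change is declared with reasons, and no between-group inference is planned. The measure had been removed by February 2017, before the interim cut-off of 16 November 2017, so nothing suggests the removal was driven by results. That stands.

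The SAP also supplies partial remedies. Total patient-years are summarised by arm for the entire granule period (Section 2.4.1), so a reader can divide any AE count by them. The disclosure tables (Section 2.7.3) put granule core, granule extension and cross-over extension in separate columns, which removes the 48-week offset. Both count as mitigation. However, dividing by total patient-years is the formula that over-corrects for common events. The disclosure tables give no rates, cover only serious AEs and non-serious AEs above 5%, and leave variable follow-up and different prior granule exposure in place.

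The core-phase reason is also fair as far as it goes. Planned core duration is equal, and crude core percentages stay reasonably comparable if early stopping is similar in the two arms. The documents give no discontinuation figures by arm.

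A reader might infer that the granule column carries about 48 weeks more follow-up and will therefore look worse. The documents do not support that. Cross-over patients must have completed the core to enter the extension (protocol Section 5.2, criterion 5), while Safety Set 4 keeps granule-arm patients who stopped early. As step 3 shows, the mean gap may shrink or reverse.

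Nor should the 32% against 18% case be taken as typical. According to the protocol's Amendment 6 rationale, 67 patients were still in the extension on 24 June 2021 and all patients had finished the core by 18 December 2018, so those 67 were about 2.5 years or more past their core phase.

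**Conclusion.** The point holds as a reporting weakness that should be corrected. A protocol commitment is withdrawn while the display that needs it is kept, and the SAP itself concedes unequal follow-up. The crude Safety Set 4 percentages mix risk with observation time.

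The size is uncertain. With equal true rates of 0.2 per patient-year and full entry into the extension, the artefact is about 14 percentage points at 52 weeks of extension (31.8% against 18.1%) and about 6 at 256 weeks (68.8% against 62.5%). Partial entry shrinks or reverses it. Event rates, extension times and entry shares are all assumptions, as is a rate that stays constant over time. No primary or secondary efficacy conclusion is affected.

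**What to change.** Revise the Table 4-1 row instead of simply deleting it. For Safety Set 4 over the entire granule period, present by arm the number of patients with an event divided by person-time to first event, censored at the end of the on-treatment period, for overall AEs, serious AEs, AEs of special interest and AEs by preferred term. State in that row that the denominator differs from the protocol's total treatment time, and why: total treatment time over-corrects for common events. Keep the crude percentages alongside.

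The inputs, AE onset dates and dosing dates, are already collected. The cost is a few extra tables and a separate person-time derivation for each event category. The patient-years in the final SAP's exposure table (Table 2-2, Section 2.4.1) cannot be reused, because they do not stop at the first event.

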## 5 Appendix

### 5.1 Imputation rules

#### 5.1.1 Study drug

The following rule should be used for the imputation of **date of last administration**:

Scenario 1: If the date of last administration is completely missing and there is no EOT eCRF page, the patient is considered as on-going. The patient should be treated as on-going and the cut-off date should be used as the last dosing date.

Scenario 2: If the date of last administration is completely or partially missing and the EOT eCRF page is available (prior to any death date or withdrawal of consent date, if available):

Case 1: The date of last administration is completely missing, and the EOT visit date is complete, then the EOT date should be used.

Case 2: Only Year(yyyy) of the dose end date is available and yyyy < the year of EOT date:

Use **Dec31yyyy**

Case 3: Only Year(yyyy) of the dose end date is available and yyyy = the year of EOT date:

Use **EOT date**

Case 4: Both Year(yyyy) and Month (mm) are available for the date of last administration, and yyyy = the year of EOT date and

mm < the month of EOT visit:

Use **last day of the Month (mm)**

mm = the month of EOT visit:

Use **EOT day**.

After imputation, compare the imputed date with the start date of that specific record, if the imputed date is < start date of that record

Use the start date of that record.

Patients with missing start dates are to be considered missing for all study treatment component related calculations and no imputation will be made. If the date of first administration is missing, then the date of last administration should not be imputed.

Note: In order to handle partial start dates issue when identifying extension phase treatment start date, “record number” and “extension” variables will be used to identify the first DAR record in extension phase. More details in PDS.

There will be no attempt to impute any other date from eCRF DAR page.

In the rare cases that there is missing EOT eCRF pages, EOT date will be imputed using the last non-zero DAR record.

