### **6.2.2 Treatment interruption and treatment discontinuation**

Patients who permanently discontinue study drug before completing the core phase should be scheduled for an End of Treatment visit within 7 days from last dose, at which time all of the assessments listed for the End of treatment visit will be performed. Patients discontinuing the optional extension phase at any time need to be scheduled for an End of Treatment visit within 7 days of the last dose. The End of Treatment eCRF should be completed for all patients at the end of both the core and the optional extension treatment phases, documenting the date and reason for stopping randomized study treatment. For the core phase the patient will be asked if they are continuing on to the optional extension phase. Any safety finding that leads to discontinuation of study drug should be captured on the AE eCRF.

All patients who discontinue study drug, including those who refuse to return for an End of treatment visit, will be contacted by the investigational site for safety evaluations during the 30 days following the last dose of study drug and the Study Evaluation Completion eCRF should be completed.

Patients who discontinue study drug should be considered withdrawn from the study after the final visit assessments are performed or when it is clear that the patient will not return for these assessments.

All patients must be followed for AEs and SAEs for 30 days after the last dose of study treatment. Patients lost to follow up should be recorded as such on the eCRF. For patients who are lost to follow-up, the investigator should show “due diligence” by documenting in the source documents steps taken to contact the patient, e.g., dates of telephone calls, registered letters, etc.

[figure not shown]

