Completion of this study as a whole will occur upon the availability and accuracy verification of the last data point required for statistical analysis of the optional extension phase. Data collection will terminate and End of Study will be declared after all patients have completed the treatment phase of the optional extension phase (up to 305 weeks) including the safety follow-up period (30 days after treatment discontinuation). The final CSR will be based on the core and extension phase using the entire granule treatment unless mentioned otherwise. **Analyses that were presented in the primary CSR or EoC CSR and for which no additional data was collected** since previous analysis data cut-off date (e.g. baseline demographics) **will not be repeated for the final analysis**. Any analyses already presented in the primary or EoC CSR will **only be repeated** in the final CSR **in case of any additional data or data changes**.

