### 2.1 Data analysis general information

Data will be analyzed by Novartis Oncology Biostatistics and Statistical Programming personnel according to the data analysis section 10 of the study protocol as detailed in this analysis plan.

SAS® version 9.4 (or later version if available at time of database lock) will be used for all analyses. Data from all patients who signed informed consent and who received granule treatment will be used in the analysis. Data collected after patients' withdrawal of informed consent for further participation in the study will not be reported (except for death date which might be obtained from public records per local laws).

All statistical analyses will be performed using all data (for patients who received granule treatment) collected in the database up to the last patient last visit (LPLV) date.

All events with a start date before or on the LPLV date and not having documented end date will be reported as 'ongoing'. This approach applies to adverse event and concomitant medication reports. For these events, the end date will not be imputed and therefore will not appear in the listings.

The time periods defined in [Table 2-1](#) will be used to define the extension phase for the analysis.

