**Table 2-2 Deferasirox: Study drug exposure**

Overall duration of exposure (day):	$[(\text{date of last exposure}) - (\text{date of first study treatment}) + 1]$
Overall duration of exposure (months)	$[(\text{date of last exposure}) - (\text{date of first study treatment}) + 1]/30.4375$
Drug exposure on dose X (days)	$[(\text{date of last exposure on dose X}) - (\text{date of first study treatment on dose X}) + 1]$
Total patient-years (years):	Overall duration of exposure (days) / 365.25
Average dose (planned and actual, in mg/kg/day):	Mean dose over all days between first and last dose, excluding interruptions: sum of all (X dose * corresponding duration of exposure on dose X) / overall number of dosing days
Cumulative dose (planned and actual, in mg/kg):	Sum over daily doses of all days between first and last dose
Percentage of planned dose taken:	$100 \times [\text{Cumulative actual dose} / \text{Cumulative planned dose}]$

For patients who switch from DT to granules in the extension phase, date of last exposure of study drug in core phase refers to the day prior to the date of the first administration of granules in extension phase (including a zero actual dose) as defined in [Table 2-1](#).

For patients who switch from DT to granules, the date of the first administration of study drug (granules) refers to the first date of granules in the extension phase (including a zero actual dose) to account for treatment interruptions due to efficacy and safety reasons. The last exposure of the granules refers to the last date when a non-zero actual dose of granules was administered during the study extension phase as defined in [Table 2-1](#).

For patients receiving granules throughout the study, the date of the first administration and last exposure of study drug refer to the first and last dates respectively when a non-zero actual dose of study drug (granules) was administered during the study.

Overall duration of exposure and total patient-years will be summarized by treatment arm for the entire granule period.

The following variables will also be summarized by treatment arm and for each phase as appropriate as:

- Duration of exposure will be categorized in the entire granule period as: <6 months, 6-<12 months, 12-<24 months, 24-<36 months, 36-<48 months and so on.

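### Final SAP 5.1.1 holds two incompatible rules for a patient with no last-dose date and no EOT page, and one of them doses the patient to an undefined cut-off

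*SAP*

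**What the plan says.** The final SAP (dated 21-Feb-2024, before database lock) sets its rules for the date of last administration in section 5.1.1.

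- Scenario 1: "If the date of last administration is completely missing and there is no EOT eCRF page, the patient is considered as on-going". It continues: "The patient should be treated as on-going and the cut-off date should be used as the last dosing date".
- Scenario 2 applies when the EOT page is available. Its Case 1 reads: "The date of last administration is completely missing, and the EOT visit date is complete, then the EOT date should be used".
- The section closes with: "In the rare cases that there is missing EOT eCRF pages, EOT date will be imputed using the last non-zero DAR record".

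Scenario 1 stands in the same form in the primary SAP (4.8.5) and the End of Core Phase SAP (4.7.3). The closing sentence appears in neither.

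On timing, final SAP 2.1 uses all data "collected in the database up to the last patient last visit (LPLV) date". Section 1 says that "End of Study will be declared after all patients have completed the treatment phase of the optional extension phase (up to 305 weeks"; the sentence goes on to include the 30-day safety follow-up. Section 1 gives calendar cut-offs for the interim, primary and End of Core analyses, but none for the final one.

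On use, section 2.4.1 states: "Overall duration of exposure and total patient-years will be summarized by treatment arm for the entire granule period". Section 2.1.6 ends the on-treatment period 30 days after the last dose.

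**The concern.** Scenario 1 made sense at the earlier analyses, when patients really were on treatment at the cut-off. Protocol Amendment 6 records 67 patients ongoing on 24-Jun-2021, after the End of Core cut-off of 18-Jan-2021. At the final analysis nobody is on treatment. A patient with neither a last-dose date nor an EOT page is then an incomplete record, not an ongoing patient.

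Scenario 1 nevertheless credits such a patient with dosing up to the cut-off, while the closing sentence points to the last dosing record. Two programmers could each follow the section and reach last-dose dates years apart. Extension-phase safety is the secondary objective marked for full reporting in the final study report (Table 1-1). Exposure duration and the on-treatment window frame those safety results.

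**Working it through.** The documents give no exposure figure for this point, so there is nothing to reproduce. The check sets the rules side by side and then sizes the difference.

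**1. Same patient, two answers** (last-dose date completely missing, no EOT page)

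| Rule in final SAP 5.1.1 | What it turns on | Resulting last dose |
|---|---|---|
| Scenario 1 | no EOT page | cut-off date |
| Closing sentence, then Scenario 2 Case 1 | EOT date from last non-zero DAR record | that DAR date |

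The closing sentence does not clearly override Scenario 1. It supplies an EOT date, whereas Scenarios 1 and 2 turn on whether the EOT page exists. Read literally, Scenario 1 still applies, and a patient could have an EOT date from the DAR and a last-dose date years later. Nor does it say which date of the DAR record to use. By section 2.1.3 the last administration is itself the last non-zero DAR date, so that record's end date may be the missing item.

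**2. Can anyone be ongoing?** No. Sections 1 and 2.1 place the analysis after all treatment and follow-up. The disposition summary agrees: End of Core SAP 2.5 had a row for patients ongoing in the extension, and final SAP 2.3.1 does not.

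**3. What uses the imputed date**

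- Affected: duration of exposure, its categories and patient-years (2.4.1, Table 2-2). Also the on-treatment window (2.1.6), and through it the safety summary tables (2.7), on-treatment deaths (2.7.2), disclosure tables (2.7.3) and worst on-treatment values (5.3.2).
- Not affected: average dose and its categories, cumulative dose and percentage of planned dose, which need complete DAR dates (2.4.1). Exposure-adjusted adverse event incidence is not presented (Table 4-1).

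**4. Size if Scenario 1 is applied**

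Duration is last exposure minus first treatment plus 1 day, so an error in the last date passes through one for one:

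excess (years) = (cut-off − true last dose) / 365.25

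Assumption: the cut-off equals LPLV, taken as 18-Dec-2018 (all core treatment complete, Protocol Amendment 6) + 5 years + 30 days = 17-Jan-2024. The true last-dose dates below are illustrative.

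| True last dose | Days to 17-Jan-2024 | Excess (years) |
|---|---|---|
| 30-Jun-2017 | 2392 | 6.55 |
| 18-Dec-2018 | 1856 | 5.08 |
| 30-Jun-2020 | 1296 | 3.55 |
| 18-Jan-2021 | 1094 | 3.00 |
| 31-Dec-2022 | 382 | 1.05 |
| 30-Sep-2023 | 109 | 0.30 |

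Sensitivity for the 18-Jan-2021 case: 2.00 years with the cut-off at 17-Jan-2023, and 3.09 years with it at the SAP date.

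**5. Size under the closing sentence**

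Nothing is carried to the cut-off. If the record's start date has to be used and the record covers one four-week dispensing interval (an assumption), the error is an under-count of at most about 28 / 365.25 = 0.08 year. The documents do not say how long a DAR record runs; a longer record at constant dose would allow a larger under-count.

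**The case against.** The best defence is that the closing sentence was added for this analysis and the ongoing row was dropped from disposition. Both suggest that the sponsor knew nobody would be ongoing and meant the DAR record to govern. On that reading Scenario 1 is a harmless leftover. That is a fair guess at intent, but the text gives no precedence and the two rules turn on different things (page versus date), so the conflict remains.

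A reader might go further and infer that the plan gives patients lost to follow-up years of granule exposure that never happened. The documents do not support that:

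- The carry-forward is one branch of an unresolved conflict, not the plan's settled outcome.
- Being lost does not trigger Scenario 1. It needs a completely missing last-dose date and also no EOT page. Protocol 6.2.2 says: "The End of Treatment eCRF should be completed for all patients at the end of both the core and the optional extension treatment phases".
- No document shows that any patient qualifies, and 5.1.1 itself calls missing EOT pages rare. The restriction of dose summaries to patients with complete DAR dates covers every start and end date, so it says nothing about how often the final one is missing.
- The size depends on when treatment really stopped, so no single case stands for the rest. The largest gives an excess above the longest planned treatment (48 weeks + 5 years = 5.92 years), which a data review might catch.

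The consequences are also bounded. All deaths are summarised and listed, all safety data are listed whatever the period, and no adverse event rate uses these patient-years as its denominator.

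**Conclusion.** The conflict is real, and one of the two rules is wrong for this analysis wherever it is applied. If Scenario 1 is programmed, each affected patient's exposure duration, duration category, patient-years and on-treatment window are overstated by the gap from true last dose to cut-off. That is about 0.30 to 6.55 years in the worked cases, given the assumed LPLV. Neither the LPLV date nor the number of affected patients is in the documents; the number may be zero. Dose-intensity results are untouched. The point calls for correction because the text permits results that differ by years, not because such a result is shown to occur.

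**What to change.** Delete Scenario 1 from final SAP 5.1.1. State that when the last-dose date is completely missing and there is no EOT page, the last non-zero DAR record governs: use its end date or, if that is missing, its start date. Do not extend dosing to a later visit, contact, cut-off or LPLV, since each would credit exposure beyond the dosing records. Either define the cut-off date for the final analysis or replace the term with LPLV where it is still used elsewhere in section 5.1. Flag these patients in the exposure listing.

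The cost is one paragraph of SAP wording and a small programming change before lock. The downside is a slight under-count of exposure for these patients, about one dispensing interval if a DAR record covers four weeks.
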